### 7.3 Randomization

Patients will be randomized in a 1:1 ratio to arms 1 and 2, respectively. Block randomization within site with random block sizes of 2, 4 or 6 will be employed.

## 7.4 Safety and Futility Monitoring

## 7.4.1 Safety monitoring

Dose Limiting Toxicity (DLT) is defined as an adverse event which: i) is determined to be at least possibly related to treatment with pembrolizumab; ii) occurs within the first 30 days after the first pembrolizumab infusion; and iii) meets one of the below criteria:

- Pneumonitis Grade  $\geq$  3
- Any non-hematological toxicity Grade  $\geq$  3, except for the following:
  - Grade 3 toxicity that is expected from standard of care cisplatin and radiation
  - Grade 3 Colitis, hypophisitis, or hyperthyroidism lasting less than 7 days
  - Grade 3 electrolyte toxicities that are corrected to grade 1 or less within 24 hours
  - Grade 3 hypertension that can be controlled with oral medications and does not require treatment delay for > 7 days
  - Grade 3 diarrhea that is not refractory to anti diarrhea medications and is corrected to Grade 1 or less within 48 hours
  - Grade 3 nausea and vomiting that is not refractory to anti-emetic therapy and is corrected to Grade 1 or less within 48 hours
  - Grade 3 rise in creatinine, if corrected to Grade 2 or less after up to 2 liters of intravenous fluids within 24 hours
  - Grade 3 elevation in AST/ALT if < 1.5 times the baseline level
  - Grade 3 elevation of ALP (alkaline phosphatase)
  - Grade 3 hypoalbuminemia
  - o Grade 3 lymphopenia

- Grade 3 rash if it returns to ≤ grade 2 after 1 week of symptomatic treatment
- Any Grade ≥ 4 toxicity
- Other AEs if they are clearly related to pembrolizumab and are causing substantial morbidity for subjects, as determined by the study chair.

Within each arm, safety will be assessed by monitoring the number of patients who experience a DLT. Results reported in ASCO 2015 abstracts [22, 23] for pembrolizumab in combination with other treatments resulted in an overall DLT rate of 1/59=2% with a 90%Cl(1%, 8%). For this study the upper boundary of a sequential probability ratio test (SPRT) based upon a binomial test of proportions for DLT will be used for monitoring to protect against excessive failure rates. The stopping boundary is for a SPRT contrasting a 5% versus 25% DLT rate, with nominal type I and II errors of 10% and 10%, respectively. The slope of the parallel line for monitoring is 1.190 and the intercept is 0.128.

Safety stopping guidelines for the occurrence of DLTs are detailed in the following table. If a stopping bound is crossed in either arm then accrual to the study will be suspended until the study PI, co-investigators and the DSMC can review the data, and determine if the study should continue, be amended or be closed to further accrual.

Incidence of treatment related DLTs	
Number of patients in an Arm	Stopping boundary
2-6	≥ 2
7-14	≥ 3
15-21	≥ 4
22-29	≥ 5
30-37	≥ 6
38-44	≥ 7

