## 3.0 OBJECTIVES & HYPOTHESES

#### 3.1 Primary Objectives

- (1) To estimate the immunologic effects, as assessed in the tumor & PBMC, of both sequential and concurrent administration of pembrolizumab to CRT. Change between pre and post measurements of HPV E2, E7 specific CD8+ T cells, regulatory FoxP3+ T cells (Tregs) and the ratio of CD8+ T cells to Tregs are the immune measurements of primary interest.
- (2) To determine the safety of concurrent chemoradiation in combination with pembrolizumab for the treatment of locally advanced cervical cancer.

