## 6.0 TRIAL FLOW CHART

## 6.1 Study Flow Chart

# 6.1.1 Arm 1

Trial Period:	Pre- Study	Treatment		Post-treatment		Survival
Visit:	Screening	CRT	Pembro	EOT visit 	Imaging	Follow-
Scheduling Interval:	-42d-1d	W1-W8	W9-W15	35 ± 5d	12w ± 10d post-CRT	Up 
Administrative Procedures						
Informed Consent/ IE	Х					
Demographics/Medical History	Х					
Concomitant Medication Review	Х					
Disease Status						Х
Survival Status						Х
Study Treatments						
Cisplatin		Х				
Radiation		Х				
MK-3475 administration			x 			
Specimen Collection						
Tissue Collection 	Х	x 			Х	
Research Blood Collection	Х	X 			Х	
Clinical Procedures/ Laboratory Assessments						
Pregnancy Test (Urine or Serum) 	х					
Review Adverse Events	Х	Х	Х	Х		

<sup>1 All subjects should be followed for 5 years following treatment to monitor disease status and overall survival. There are no per protocol assessments, all subjects should be monitored according to the standard of care of the treating physicians.

<sup>2 Each subject should return to the clinic for a visit 30-40 days following the last study treatment (of either pembrolizumab or chemoradiation) for assessment of adverse events

<sup>3 Pembrolizumab treatment should be scheduled for every 21 days ( $\pm$  3 days) starting on Week 9.

<sup>4 Fresh tissue biopsies are required. If archival tissue is available these may also be submitted to supplement fresh tissue collected at baseline.

<sup>5 Tissue and blood specimen collected during CRT interval should be obtained at  $5 \pm 2$  weeks

<sup>6 Women of childbearing potential must have a negative pregnancy test within 72 hours of first dose of study treatment.

Trial Period:	Pre- Study	Treat	tment	Post-tre	Survival		
Visit:	Screening	CRT	Pembro	EOT visit 	Imaging	Follow-	
Scheduling Interval:	-42d-1d	W1-W8	W9-W15	35 ± 5d	12w ± 10d post-CRT	Up 	
Physical Examination/ECOG	X7	X 	X 	х	X 		
Vital Signs	Х	Х	Х	Х			
PT/INR and aPTT 	Х						
CBC with Differential 	Х	x 	X 	Х			
Serum Chemistry Panel 	Х	X 	X 	Х			
Thyroid panel 	Х		X 	Х			
	Tumor Imaging/Disease Assessments						

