Pregnancy Test (Urine or Serum) 	х				
Review Adverse Events	Х	Х	Х		
Physical Examination/ECOG	X 	X 	х	X 	
Vital Signs	Х	Х	Х		

<sup>1 All subjects should be followed for 5 years following treatment to monitor disease status and overall survival. There are no per protocol assessments, all subjects should be monitored according to the standard of care of the treating physicians.

<sup>2 Each subject should return to the clinic for a visit 30-40 days following the last study treatment (of either pembrolizumab or chemoradiation) for assessment of adverse events

<sup>3 Pembrolizumab treatment should be scheduled for every 21 days ( $\pm$  3 days) starting on Day 1.

<sup>4 Fresh tissue biopsies are required. If archival tissue is available these may also be submitted to supplement fresh tissue collected at baseline.

<sup>5 Tissue and blood specimen collected during CRT interval should be obtained at  $5 \pm 2$  weeks

<sup>6 Women of childbearing potential must have a negative pregnancy test within 72 hours of first dose of study treatment.

<sup>7 Physical exam at screening and at the time of the post-treatment imaging should include a clinical tumor assessment

<sup>8 Physical exams should be done at a minimum every 3 weeks during study treatment interval

Trial Period:	Pre- Study	Treatment	Post-tre	eatment	• • •
Visit:	Screening	CRT + MK-3475	EOT visit 	Imaging	Survival Follow-
Scheduling Interval:	-42d-1d	W1-W9	(35 ± 5d)	12w ± 10d post-CRT	Up 
PT/INR and aPTT 	Х				
CBC with Differential 	Х	x 	Х		
Serum Chemistry Panel 	Х	X 	Х		
Thyroid panel 	Х	X 	Х		
Tumor Imaging/Disease As	sessments				
MRI 	Х				
PET/CT 	Х			Х	

<sup>9 Prior to first day of treatment (Day 1 Week 1), laboratory tests do not need to be repeated if screening labs were performed within 14 days prior to treatment date.

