# 6.4.1.1 Expectedness

The expectedness of the adverse event will be determined by the Investigator based on current literature, the Investigator's Brochure or package insert and the Investigator's experience. Adverse events commonly observed with the standard of care chemoradiation treatment, such as hematological, genitourinary and gastrointestinal, should be expected during the CRT interval.

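### The DLT rule may not register a rise in Grade 3 chemoradiation toxicity in Arm 2, and section 7.5 plans no use of Arm 1 Weeks 1–8 as the randomised CRT-only control

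*Combined protocol and SAP*

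**What the plan says.** The second primary objective in section 3.1 is "To determine the safety of concurrent chemoradiation in combination with pembrolizumab".

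The only quantitative safety rule is in section 7.4.1. DLTs are counted within each arm against a sequential boundary that contrasts 5% with 25%. Every DLT must be an event that "is determined to be at least possibly related to treatment with pembrolizumab" and that "occurs within the first 30 days after the first pembrolizumab infusion". It must also meet one of four criteria: pneumonitis of Grade 3 or higher; non-hematological toxicity of Grade 3 or higher, subject to a list of exceptions; "Any Grade ≥ 4 toxicity"; or a catch-all judged by the study chair. The first exception on the list is "Grade 3 toxicity that is expected from standard of care cisplatin and radiation".

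Section 6.4.1.1 is the only place that describes what is expected from CRT: "Adverse events commonly observed with the standard of care chemoradiation treatment, such as hematological, genitourinary and gastrointestinal, should be expected during the CRT interval". It gives no rate and does not mention DLTs.

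Sections 2.1 and 5.3.3.3 give both arms the same CRT. The flow charts schedule pembrolizumab "starting on Week 9" in Arm 1 (6.1.1) and "starting on Day 1" in Arm 2 (6.1.2). Section 7.1.1 lists adverse event incidence and severity as a safety endpoint alongside DLTs. Section 7.5 describes no adverse event analysis, within or between arms.

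**The concern.** In Arm 2 the toxicities that concurrent pembrolizumab could plausibly make more frequent are partly those that CRT already causes. Three features of the DLT definition can keep such an increase out of the count: the exemption for expected Grade 3 events, the lack of a Grade 3 hematological criterion, and a 30-day window that is shorter than the CRT course. Each case also has to be attributed to one component of an open-label combination.

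Randomisation offers a way round case-by-case attribution. Until Week 9 the arms differ by design only in whether pembrolizumab is given, so the difference in event rates estimates its effect on CRT toxicity. If the plan does not ask for that estimate, a primary objective will rest on an attributed, within-arm count and on adverse event summaries with no prespecified contrast.

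**Working it through.** **1. The plan's boundary reproduces.** Inputs from 7.4.1: p0 = 0.05, p1 = 0.25, both error rates 0.10.

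- D = ln[0.25 × 0.95 / (0.05 × 0.75)] = ln(6.333) = 1.846
- Slope = ln(0.95/0.75)/D = 0.2364/1.846 = 0.128
- Intercept = ln(0.90/0.10)/D = 2.197/1.846 = 1.190

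Rounding 1.190 + 0.128n up to the next integer gives all six rows of the stopping table. The text swaps the words slope and intercept, which does not affect the table.

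**2. What the boundary can see.** These are exact binomial probabilities of crossing by n = 44, checking the table after each patient from n = 2.

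| True rate of counted DLTs | 5% | 10% | 15% | 20% | 25% | 30% |
|---|---|---|---|---|---|---|
| P(cross) | 6.3% | 32% | 66% | 88% | 97% | 99.5% |

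Assume a base DLT rate of 5% and a pembrolizumab-caused excess e of expected-type Grade 3 toxicity, of which a fraction f is counted. The counted rate is then 5% + f × e.

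| Excess e | None counted (f = 0) | Half counted | All counted |
|---|---|---|---|
| 10 points | 6.3% | 32% | 66% |
| 20 points | 6.3% | 66% | 97% |
| 30 points | 6.3% | 88% | over 99% |

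The documents fix neither e nor f. The table shows how far the rule's behaviour depends on how investigators read the exemption.

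**3. Timing.** Weeks 1–8 are 56 days, and all radiation must be delivered within 8 weeks. In Arm 2 the DLT window covers roughly the first 30 of those days. Infusions fall on about Days 1, 22 and 43 (1 + 2 × 21), so the third lies outside it. Later CRT events are not DLTs at any grade. In Arm 1 the window opens in Week 9, so its CRT-only period never enters DLT monitoring.

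**4. What the randomised comparison would give.** The documents state no Grade 3 rate for CRT, so a background p of 20% to 50% is assumed. With equal rates in both arms, the 90% CI half-width for the difference is 1.645 × √[2p(1−p)/n].

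| p | n = 44 per arm | n = 49 per arm |
|---|---|---|
| 20% | 0.140 | 0.133 |
| 30% | 0.161 | 0.152 |
| 50% | 0.175 | 0.166 |

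The 44 is the evaluable number per arm in 7.2. The 49 is half the maximum accrual of 98, and is relevant because the safety set is all treated patients.

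As a guide to the excess that could be distinguished, use the normal approximation Φ[(Δ − 1.2816 × SE0)/SE1], with SE0 pooled and SE1 unpooled, at one-sided 10% and 44 per arm. Over backgrounds of 20% to 50%, power is 37–42% for +10 points, 73–78% for +20 and 95–96% for +30. For +20 points the exact Fisher test gives 67–71% at backgrounds of 20–40%.

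**The case against.** **A reader might infer that the exemption hides any increase in CRT toxicity.** The documents do not support that. Attributed events of Grade 4 or higher and Grade 3 pneumonitis within the window still count, and so may events caught by the study chair's criterion. Adverse event incidence and severity is an endpoint in all treated patients (7.1.1). The Data and Safety Monitoring Committee (DSMC) reviews aggregate adverse events monthly (6.4.5.1), and section 5.7.4 allows early termination on the incidence or severity of adverse drug reactions without a DLT count. An increase could escape the DLT rule, not the data. Equally, Arm 1's CRT period is not ignored for safety: its events are collected and reviewed. What is missing is a prespecified contrast.

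**A reader might also infer that every Grade 3 gastrointestinal or genitourinary event is exempt.** That is only one reading. Section 6.4.1.1 concerns adverse event assessment in general and leaves expectedness to the investigator. The list in 7.4.1 separately exempts Grade 3 diarrhea and nausea or vomiting only if corrected within 48 hours, and creatinine rise only if corrected within 24 hours. Those limits would be largely redundant under a blanket exemption. Grade 3 hematological events are outside the main criterion because it is restricted to non-hematological toxicity, not because they are called expected.

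**The exemption has a purpose.** If CRT events with a 30% background were all counted as DLTs, the boundary would be crossed with probability 99.5% from background alone. Deleting it would not be a clean remedy.

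**Attribution has rules.** Section 5.5.1 gives features that point to immune-related diarrhea or colitis, and 6.4.4.2 requires other causes of possible immune-related events to be ruled out. These help with individual cases. They do not estimate an excess of events that look like ordinary CRT toxicity.

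**The design is non-comparative.** The statement in section 7.0 that no definitive between-arm comparison is intended is framed around CD8+ and regulatory T cells. Section 7.5 already plans between-arm estimates of immune change, so an estimated safety difference is in keeping with it.

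**The comparison has limits.** Only Arm 2 has liver function and thyroid tests scheduled during CRT, so an overall count would be unequally ascertained. Open-label reporting can still influence grading. Precision is modest. All three points stand and shape the fix.

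**Conclusion.** The concern holds in a limited form. A pembrolizumab-caused rise in Grade 3 gastrointestinal, genitourinary or hematological toxicity during CRT in Arm 2 may not move the DLT rule, and the plan prespecifies no use of the randomised CRT-only control that would show it.

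In the extreme case where none of a 20-point excess is counted, the crossing probability stays at 6.3% instead of 97%; counting half gives 66%. These figures assume a 5% base DLT rate and an excess of that size. The fraction exempted cannot be determined from the text. The missing estimate would have a 90% half-width of about 14 to 18 points with 44 per arm, under assumed background rates of 20% to 50%. It is therefore useful for estimation and for large excesses, and weak for an excess of 10 points.

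This is an omission from the analysis plan. It does not show that the trial is unsafe or that toxicity data are concealed.

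**What to change.** Leave the DLT definition and boundary as they are. The sponsor should reconcile, within the 7.4.1 list, whether the exemption for expected Grade 3 toxicity overrides the 48-hour and 24-hour limits; this review takes no view on which should govern.

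Add to section 7.5, and to the DSMC report displayed by arm:

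- the Arm 2 minus Arm 1 difference, with 90% CI, in the proportion of treated patients with at least one Grade 3 or higher adverse event with onset in Weeks 1–8, regardless of attribution and analysed by randomised arm;
- the same difference separately for gastrointestinal, genitourinary and hematological classes;
- an overall figure that excludes liver and thyroid laboratory events, with the unequal testing schedule given as the reason;
- a statement that this is estimation, not a hypothesis test, with the expected half-widths.

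The cost is one table. Section 6.4.4.3 already requires Grade 3 to 5 events to be entered in OnCore whatever their attribution, and both flow charts schedule adverse event review during CRT. No new data, patients or visits are needed.

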## 5.7.3 Subject Status Definitions

Enrolled: All subjects who sign an informed consent will be considered enrolled on the study. All subjects consented on the study must be entered into OnCore.

Screen Failure: A subject who is withdrawn or discontinues from the study prior to receiving any treatment is considered a post enrollment screen failure. Post enrollment screen failures are not considered a study accrual and will be replaced. Note: The UVa IRB-HSR defines any individual that has signed an informed consent as an enrollment in this study and so screen failures should be reported to the IRB with enrollment numbers.

Protocol/Amendment No.: UVA-LACC-PD201, Version 4.0, 06 March 2018

On-Study: A subject is considered on-study on the date when the study team has confirmed the subject has met all of the inclusion and none of the exclusion criteria, and the treating physician/surgeon or study PI has signed off on the confirmation.

Randomized: A subject that has been randomized to an arm is considered a randomized subject.

On-Treatment: A subject is considered on-treatment on the date that CRT is initiated

Off-Treatment: A subject is considered off-treatment on the date that they have met any of the criteria listed in Section 5.7.1

On Follow-up: A subject is considered on follow-up on the date that they have met any of the criteria listed in Section 5.7.1.

Off-Study: A subject is considered off-study if they are removed from the study for any of the reasons listed in Section 5.7.2, or if they have completed the follow-up interval.

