### 7.1 Evaluation Criteria

## 7.1.1 Safety Endpoints

All patients receiving any protocol treatment will be evaluated for safety. Safety assessments will include:

- i. Incidence and severity of adverse events.
- ii. Incidence of dose limiting toxicities (DLT) defined in section 7.4.

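### The DLT stopping line is printed with slope and intercept exchanged, and the stopping table does not say which patients it counts

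*Combined protocol and SAP*

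**What the plan says.** Section 7.4.1 monitors DLTs within each arm using the upper boundary of a binomial SPRT that contrasts a 5% with a 25% DLT rate, with nominal type I and II errors of 10% each. It then states: "The slope of the parallel line for monitoring is 1.190 and the intercept is 0.128". The stopping table follows: at least 2 DLTs at 2-6 patients, 3 at 7-14, 4 at 15-21, 5 at 22-29, 6 at 30-37 and 7 at 38-44. Crossing in either arm suspends accrual to the whole study pending review.

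The table's first column is headed only "Number of patients in an Arm". Other sections bear on what that means:

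- Section 7.1.1: "All patients receiving any protocol treatment will be evaluated for safety". Its list of safety assessments includes "Incidence of dose limiting toxicities (DLT) defined in section 7.4".
- Section 5.7.3: "A subject is considered on-treatment on the date that CRT is initiated".
- Section 7.4.1: a DLT must be an event that "occurs within the first 30 days after the first pembrolizumab infusion".
- Sections 6.1.1 and 6.1.2: pembrolizumab is scheduled "starting on Week 9" in Arm 1 and "starting on Day 1" in Arm 2.

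**The concern.** A slope of 1.190 DLTs per patient cannot be a usable boundary: the line rises faster than the number of patients and contradicts the table printed beneath it. Anyone who re-derives or extends the boundary from that sentence gets nonsense. An extension is foreseeable, because section 7.2 allows 98 patients, about 49 per arm, and the table ends at 44.

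The count matters more in practice. A binomial SPRT assumes that every patient counted has had a chance of the event. The only population that the plan ties to DLT incidence, in section 7.1.1, begins with CRT. In Arm 1 it therefore takes in patients who cannot yet have a DLT by definition, and it keeps any who never receive pembrolizumab. The same table would then be less sensitive in Arm 1 than in Arm 2. Two people applying it to the same data could also reach opposite decisions, and safety is a primary objective.

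**Working it through.** **The line.** Inputs from section 7.4.1: p0 = 0.05, p1 = 0.25, α = β = 0.10.

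- k = ln[p1(1−p0) / (p0(1−p1))] = ln(0.2375/0.0375) = 1.8458
- intercept = ln[(1−β)/α] / k = ln 9 / 1.8458 = 1.1904
- slope = ln[(1−p0)/(1−p1)] / k = ln(0.95/0.75) / 1.8458 = 0.1281

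The two printed numbers are right and the labels are exchanged. As printed, 0.128 + 1.190n gives 1.32 at n = 1, 2.51 at n = 2, 12.03 at n = 10 and 52.49 at n = 44, always above n.

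**The table.** Rounding 1.190 + 0.128n up to a whole number reproduces all 43 entries from n = 2 to 44. Two of the steps: n = 6 gives 1.958, so 2, and n = 7 gives 2.086, so 3; n = 21 gives 3.878, so 4, and n = 22 gives 4.006, so 5. Beyond the table, n = 45 gives 6.95 (7), n = 46 gives 7.078 (8) and n = 49 gives 7.462 (8).

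If patients are assessed one at a time, the exact probability that the table is crossed by n = 44 is 6.3%, 32.1%, 66.1% and 97.1% at true DLT rates of 5%, 10%, 15% and 25%.

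**How many are counted too early.** Section 7.2 plans 4 patients a month, so about 2 per arm. Week 1 to Week 9 is 8 weeks: 56/30.44 = 1.84 months, and 2 × 1.84 ≈ 3.7 Arm 1 patients in the count before any pembrolizumab. As an example, 2 DLTs among 6 exposed patients crosses (boundary 2). With 4 more patients on CRT counted, n = 10 has boundary 3 and does not cross.

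**Effect on the rule.** Simulation with 80,000 runs. Assumptions: 2 patients per arm per month arriving at random, an 8-week lag in Arm 1 and none in Arm 2, DLTs spread evenly over the 30 days, 44 per arm, all exposed. The entries are the percentage of trials crossing when the count is of treated / exposed / DLT-evaluable patients.

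| True DLT rate | Arm 1 | Arm 2 |
|---|---|---|
| 5% | 2.6 / 5.2 / 7.5 | 5.1 / 5.1 / 7.4 |
| 10% | 22.4 / 29.8 / 34.9 | 29.7 / 29.7 / 34.7 |
| 15% | 57.4 / 64.2 / 68.3 | 64.0 / 64.0 / 68.3 |
| 25% | 95.9 / 96.9 / 97.4 | 96.8 / 96.8 / 97.4 |

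At 25%, the mean number of exposed Arm 1 patients at crossing is 16.0 / 12.6 / 11.5. The Week 9 start accounts for about 7 points at 10% and 15%; the remaining 4 to 5 points come from waiting for the 30 days to end.

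**Ranges.** With lags of 6 to 10 weeks at 2 per month, and 1 to 3 per month at 8 weeks, the treated count crosses in 55-62% at a true 15% and 19-26% at 10%. The Week 9 effect is 4 to 9 points.

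**Suspension through either arm**, 1 − (1−a)(1−b) with arms independent, on the same three counts:

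- both arms at 5%: 7.6 / 10.1 / 14.3%, against 1 − (1−0.0628)² = 12.2% as designed
- both at 15%: 84.7 / 87.1 / 89.9%
- Arm 1 at 15% and Arm 2 at 5%: 59.6 / 66.0 / 70.7%
- both at 25%: 99.9% on every count

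**Never exposed.** If 10% of Arm 1 never receive pembrolizumab (an assumption that borrows the combined ineligibility and drop-out figure in section 7.2), Arm 1 crosses in 46.8 / 60.5 / 65.3% at 15% and 91.8 / 95.5 / 96.4% at 25%.

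**The case against.** The label error has no operational effect: section 7.4.1 makes the table the stopping guideline, and the table is right. That stands, and on its own this would be a correction of wording.

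The dilution depends on a reading. Section 7.1.1 says who is evaluated for safety; it does not say that this group is the sequential denominator. A binomial test with a window opening at the first infusion points towards exposed patients. This also stands, but it leaves two readings of a stopping rule. The futility rule in section 7.4.2 specifies patients accrued and followed for 12 weeks, so the plan defines its count there and not here.

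The larger losses occur at 10% and 15%, rates the plan does not design for. At 25% the eventual crossing probability barely moves, and what remains is about 3 more exposed Arm 1 patients at crossing (16.0 against 12.6). That is correct.

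Counting exposed patients would by itself cure the Week 9 problem; requiring the 30 days to end goes further and raises false crossing. This is fair as a description of the trade. The stricter count is preferred because each patient in a binomial test should have a known outcome, and its cost stays below the nominal error. The table extension matters only if an arm's count passes 44.

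Other safeguards exist: monthly DSMC review, 24-hour SAE and ECI reporting, and early termination for safety. They limit the harm, but the DSMC's remit in section 6.4.5.1 includes applying the stopping rules, so it needs a defined count.

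**Conclusion.** Both points hold. The label swap is certain, follows from the section's own inputs, and leaves the table unchanged. The table's count is undefined, and the only population linked to DLT incidence would make the rule slower in Arm 1. On that reading Arm 1 loses about 7 percentage points of crossing probability at true rates of 10% and 15% because of the Week 9 start (range 4 to 9), and about 3 more Arm 1 patients are exposed before crossing at 25%. Eventual crossing at 25% is essentially unaffected. These sizes rest on the accrual, lag and DLT-timing assumptions shown, and on counting patients from the start of CRT. The plan should be corrected; the weight rests on the undefined count rather than on the label error.

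**What to change.** 1. In section 7.4.1, give the slope as 0.128 and the intercept as 1.190.
2. Define the table's count as patients in the arm who have received pembrolizumab and have either had a DLT or ended DLT observation (30 days completed, or left earlier without a DLT).
3. Keep all existing entries and extend the table on the same line: at least 7 DLTs at 45 patients and at least 8 at 46-49.

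The cost is two wording edits and a short extension. The DLT definition, the existing boundaries and data collection do not change.

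There is a statistical price. A DLT counts at once, while a DLT-free patient counts only when observation ends, which tilts the rule towards crossing. At a true 5% rate, per-arm crossing becomes about 7.5% (range 6.5-8.0%), against 6.3% as designed, and remains below the nominal 10%. Suspension through either arm becomes about 14%, against 12% as designed. Extending to 49 leaves the per-arm figure at 7.4%. Early leavers should be counted: if 10% leave DLT-free before day 30, leaving them out gives 9.5% instead of 7.7%.

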## 5.3.2.1 Pembrolizumab Dose Modification

Modification of the dose of pembrolizumab is not allowed on this study. The dose of pembrolizumab can be delayed or withheld due to adverse events. Adverse events (both non-serious and serious) associated with pembrolizumab exposure may represent an immunologic etiology. Pembrolizumab must be withheld for drug-related toxicities and severe or life-threatening AEs as per **Error! Reference source not found.** below. See Section 5.5.1 and Events of Clinical Interest Guidance Document for supportive care guidelines, including use of corticosteroids.

Pembrolizumab should be administered once every 21 days for 3 cycles. If a delay in dosing is required per the guidelines in **Error! Reference source not found.**, then the dose may be delayed for up to 7 days. In case the toxicity does not resolve to Grade 0-1 or baseline within 7 days, the dosing on either the second or third cycle may be withheld. If the second cycle dose cannot be administered due to unresolved toxicity, then the third dose of pembrolizumab should occur on the scheduled day 1 of the third cycle (if the toxicity has resolved to Grade 0-1 or baseline). If the third dose cannot be administered due to unresolved toxicity within 7 days, then the subject may continue on study without additional pembrolizumab (may continue to receive cisplatin and RT). In general, please follow the following pembrolizumab-specific guidelines:

- i. Corticosteroid taper should be initiated upon AE improving to Grade 1 or less and continue to taper over at least 4 weeks. This criterion may also be met if the toxicity resolves to pre-study baseline grade (if toxicity was present at baseline).
- ii. For severe and life-threatening irAEs, IV corticosteroid should be initiated first followed by oral steroid. Other immunosuppressive treatment should be initiated if irAEs cannot be controlled by corticosteroids.
- iii. For situations where pembrolizumab has been withheld and the toxicity has not resolved within 7 days, the dose may be skipped. Otherwise, pembrolizumab can be resumed after AE has been reduced to Grade 1 or 0 (or baseline, as described in "i") and corticosteroid has been tapered.

Immune-related AEs	Toxicity grade or conditions (CTCAEv4.0)	Action taken to pembrolizumab	irAE management with corticosteroid and/or other therapies	Monitor and follow-up

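### Crossing a DLT bound suspends accrual but does not hold pembrolizumab, so in Arm 1, where dosing starts in Week 9, queued patients can still get a first dose before the review decides

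*Combined protocol and SAP*

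**What the plan says.** Section 7.4.1 sets the unit of monitoring: "Within each arm, safety will be assessed by monitoring the number of patients who experience a DLT". To count, an event must be at least possibly related to pembrolizumab and must be one that "occurs within the first 30 days after the first pembrolizumab infusion". The upper line of a sequential probability ratio test (5% against 25%) "will be used for monitoring to protect against excessive failure rates".

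The consequence of crossing is a single sentence: "If a stopping bound is crossed in either arm then accrual to the study will be suspended" until the PI, co-investigators and DSMC have looked at the data and can "determine if the study should continue, be amended or be closed to further accrual". No time limit is set for that review, and dosing of enrolled patients is not mentioned.

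The flow charts in 6.1 schedule pembrolizumab "starting on Week 9" in Arm 1, after CRT in Weeks 1 to 8, and "starting on Day 1" in Arm 2.

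On delays, 5.3.2.1 deals with the patient's own toxicity. It allows up to 7 days, after which "the dosing on either the second or third cycle may be withheld". Section 5.3.3.2 allows 3 days either way for administrative reasons. Section 5.3.2 does not allow dose modification for anything other than treatment-related adverse events. Section 5.7.1 lists the events that end study treatment; a crossed bound is not among them.

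**The concern.** A stopping bound should act on the exposure that it monitors. In Arm 2 it does: a patient not enrolled is a patient not infused, so suspending accrual ends almost all new exposure at once. In Arm 1, enrolment and first infusion are about 8 weeks apart. When Arm 1 crosses, patients already in CRT remain scheduled for a first dose, and even closure to further accrual would not in itself change that.

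The default elsewhere in the protocol is to dose. The delay and withholding rules concern a patient with toxicity of her own and name only the second and third cycles. A site wishing to hold the first dose of a well patient because of events in other patients has no dosing text to rely on.

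At stake is whether the next Arm 1 patients are infused, between the crossing and the review's decision, with a drug whose DLT rate has just triggered an alarm.

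**Working it through.** **Reproducing the plan's boundary.** With p0 = 0.05, p1 = 0.25 and both errors 0.10:

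- D = ln[p1(1 − p0) / (p0(1 − p1))] = ln(0.2375/0.0375) = 1.846
- intercept = ln(0.9/0.1)/D = 2.197/1.846 = 1.190
- slope = ln(0.95/0.75)/D = 0.2364/1.846 = 0.128

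Rounding 1.190 + 0.128n up gives 2 for n = 2–6, 3 for 7–14, 4 for 15–21, 5 for 22–29, 6 for 30–37 and 7 for 38–44. All six rows of the table agree. (The text of 7.4.1 attaches the names slope and intercept the wrong way round; the table is right.) The boundary itself is not in question, only what follows when it is crossed.

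**Inputs.** Accrual of 4 a month and 10% ineligibility/drop-out (7.2); 1:1 allocation (7.3); Arm 1 first dose after 8 weeks (6.1.1); doses 21 days apart (5.2). Assumption: a review of 14 to 28 days. The protocol gives only a monthly routine DSMC meeting (6.4.5.1). A month is taken as 30.4 days.

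**Patients affected**, with Arm 1 accrual of 4/2 = 2 a month:

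| Quantity | Calculation | Result |
|---|---|---|
| Arm 1 patients waiting for a first dose | 2 × 56/30.4 | 3.7 |
| First doses in a 2-week review | 2 × 14/30.4 | 0.92 |
| First doses in a 4-week review | 2 × 28/30.4 | 1.84 |
| The two review figures less 10% drop-out | × 0.9 | 0.83 and 1.66 |
| Further DLTs at a 25% rate | 0.25 × 0.92; 0.25 × 1.84 | 0.23 to 0.46 |
| Further DLTs at a 5% rate | 0.05 × 0.92; 0.05 × 1.84 | 0.05 to 0.09 |
| Patients between dose 1 and dose 3, per arm | 2 × 42/30.4 | 2.8 |

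Any review shorter than 8 weeks leaves the queue unexhausted, so the count is linear in review length. Arm 1 cannot cross until two of its patients have been infused, so accrual has by then run for at least 8 weeks. Slower accrual shrinks every count in proportion.

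**How often a hold would be triggered.** Applying the table after each patient up to 44, by exact binomial recursion, gives these crossing probabilities for one arm:

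| True DLT rate | P(cross) |
|---|---|
| 5% | 6% |
| 10% | 32% |
| 15% | 66% |
| 25% | 97% |

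**What a hold would do to the primary sample.** Arm 1 doses fall nominally on days 57, 78 and 99, and the last biopsy is 12 weeks (84 days) after CRT ends. The gap from last dose to sample is (CRT end + 84) − (99 + deferral). Patients due evenly over a hold wait half of it on average: 7 days for a 2-week hold, 14 for a 4-week hold.

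| CRT ends | No hold | 7-day deferral | 14-day deferral | 28-day deferral (worst case) |
|---|---|---|---|---|
| Day 56 | 41 days | 34 | 27 | 13 |
| Day 42 | 27 days | 20 | 13 | −1 |

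In the last cell the third dose falls on day 127, one day after the nominal sample on day 126, though inside its ±10-day window (to day 136). The share of Arm 1 affected is 0.92/44 = 2.1% to 1.84/44 = 4.2%.

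**The case against.** The strongest reply is that the bound does more than stop enrolment. It forces a review whose listed outcomes include amending the study, and an amendment can cover dosing of enrolled patients. Other routes are quick. Serious adverse events reach the Sponsor-Investigator within 24 hours (6.4.4.1). The DSMC reviews application of the stopping rules and takes immediate concerns to the PI (6.4.5.1). Subjects can be withdrawn for safety reasons (5.7). A potential health hazard is a ground for early termination (5.7.4). A change to remove an immediate hazard needs no prior IRB approval (9.2.1).

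This stands, and it limits the point. A reader might infer that the protocol leaves no means of stopping these infusions, or that the study would go on infusing the queue after a crossing. The documents do not support either reading: the PI could hold the next dose the same day. What remains is the interval before the review decides, during which a hold depends on someone choosing to act, because the bound itself triggers none of these routes except the review.

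It is also fair to say that the count rests on an assumed review length, that fewer than half an extra DLT is expected even at a 25% rate, and that leaving enrolled patients to expert review is a coherent choice. That choice is easiest to defend for mid-course patients and, when Arm 2 crosses, for the Arm 1 queue; in those cases it is enough that the review must decide. It is weaker for first doses in the arm that has just crossed, because those are the exposure that the bound is meant to limit.

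Finally, a hold is not always warranted. Quoting only the 6% crossing probability at a 5% DLT rate would understate this, since the probability is 32% at 10% and 66% at 15%.

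**Conclusion.** The concern holds in a limited form. For Arm 1 the automatic action comes about 8 weeks upstream of the monitored exposure, and no dosing text covers holding a well patient's first dose. The size is 0.9 to 1.8 first doses out of a queue of about 3.7. This assumes planned accrual, a 2-to-4-week review and no use of discretionary powers. It is an expected number, and it scales with review length and accrual.

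This is a low-priority, inexpensive improvement. It is not evidence that the boundary is miscalculated, that the monitoring fails in Arm 2, or that patients are left without protection.

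**What to change.** Add to 7.4.1, after the sentence on suspending accrual:

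- Crossing a bound also holds first pembrolizumab doses in the arm that crossed until the review concludes; standard CRT continues.
- The review must state whether dosing continues in patients between their first and third doses and, if Arm 2 crosses, in Arm 1 patients not yet infused.

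Add a one-line exception to the timing text in 5.3.3.2 so that a dose held for this reason is not a deviation. Leave the handling of late doses to the review; detailed rules on make-up doses or sample timing are not needed for so few patients.

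The drafting cost is a few sentences. The scientific cost falls on the 12-week immunologic sample: about 2% to 4% of Arm 1 would start late, with a shorter interval from last dose to sample and, in the worst case, a lost third dose. Some holds will prove unnecessary once reviewed, more often if the true DLT rate is 10% to 15% than if it is 5%. A prompt review keeps both costs down.
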